### 4.2 Safety endpoints

The assessment of safety will be based on the incidence of adverse events (AEs), serious adverse events (SAEs), adverse events leading to discontinuation, adverse events leading to dose modification, select adverse events (select AEs) for EU Submission, immune-mediated AEs (IMAEs) for US Submission, other events of special interest (OEOSI), and deaths. The use of immune modulating concomitant medication will be also summarized. In addition, clinical laboratory tests, and immunogenicity (i.e., development of anti-drug antibody) will be analyzed.

### 4.3 Other Endpoints

#### 4.3.1 Pharmacokinetics

Relatlimab and nivolumab concentration-time data at scheduled trough (Ctrough) and end-of-infusion timepoints will be evaluated. Measurements will be collected on treatment (up to 12

cycles) and for up to second post-treatment follow-up. These data may also be pooled with other dataset for population PK and exposure-response analysis which will be presented in a separate report.

#### **4.3.2 Biomarkers**

Biomarker endpoints from peripheral blood will generally be measured at multiple timepoints, and evaluated as both predictive and pharmacodynamic markers in the context of the exploratory biomarker objectives. These may include measures such as levels and change from baseline in levels of the following at each scheduled timepoint:

- Serum soluble factors including cytokines and soluble LAG3
- The proportion of specific lymphocyte subsets/expression levels of T cell co-stimulatory/inhibitory markers assessed using flow cytometry

Biomarker endpoints from tumor biopsies will be explored predominantly in an effort to identify baseline markers predictive of efficacy, since they are only measured at baseline for most subjects.

For the subset of subjects who have both pre-treatment and on-treatment biopsies, pharmacodynamic associations may be explored. Endpoints may include measures such as pre-treatment levels and change in levels observed on-treatment of:

- Expression of selected genes and gene signatures
- IHC assessment of the presence/absence and intensity of T-cell infiltration and expression of MHC I, MHC class II, CD3 and CD8
- Tumor mutation burden

Appropriate functional transformation of these exploratory measures will be applied as necessary. Measures not available at the time of the clinical study report may be summarized in a separate report.

##### **4.3.2.1 PD-L1 and LAG-3**

PD-L1 expression is defined as the percent of tumor cells demonstrating plasma membrane PD-L1 staining of any intensity using an immunohistochemistry (IHC) assay. LAG-3 expression is defined as the percent of nucleated cells demonstrating LAG-3 staining of any intensity using an immunohistochemistry (IHC) assay.

Additional biomarkers potentially associated with clinical endpoints will be measured by analyzing tumor and blood samples. Biomarker endpoints include, but are not limited to, single-nucleotide polymorphisms (SNPs), proteins in tumor specimens and serum, and immune cell populations.

PD-L1 expression and LAG-3 expression will be collected in the IRT as well as in the clinical database. Please see [Section 6.2.1](#) for more details on which values will be used for the analyses.

### 4.3.3 Immunogenicity

Incidence of ADA to either relatlimab or nivolumab will be assessed during treatment and for up to second follow-up post treatment. Baseline ADA positive subject is defined as a subject with positive seroconversion detected in the last sample before initiation of treatment. ADA-positive subject is a subject with at least 1 ADA-positive sample relative to baseline after initiation of the treatment.

At the sample level, individual samples will be characterized as ADA-positive or ADA-negative. A subject will be considered to have a positive sample at baseline if the last sample prior to the initiation of treatment is ADA-positive. To examine the potential relationship between immunogenicity and safety, a table summarizing the frequency and type of AEs of special interest may be explored by immunogenicity status.

#### 4.3.3.1 ADA Status of a Sample

- Baseline ADA-Positive Sample: ADA is detected in the last sample before initiation of treatment
- Baseline ADA-Negative Sample: ADA is not detected in the last sample before initiation of treatment
- ADA-Positive Sample: After initiation of treatment, (1) an ADA detected (positive seroconversion) sample in a subject for whom ADA is not detected at baseline, or (2) an ADA detected sample with ADA titer to be at least 4-fold or greater (1) than baseline positive titer
- ADA-Negative Sample: After initiation of treatment, ADA not positive sample relative to baseline

#### 4.3.3.2 ADA Status of a Subject

- Baseline ADA-Positive Subject: A subject with baseline ADA-positive sample
- ADA-Positive Subject: A subject with at least one ADA-positive sample at any time after initiation of treatment
- *Persistent Positive (PP)*: ADA-positive sample at 2 or more consecutive timepoints where the first and last ADA-positive samples are at least 16 weeks apart

*Not PP - Last Sample Positive*: Not persistent positive with ADA-positive sample in the last sampling timepoint

- *Other Positive*: Not persistent positive but some ADA-positive samples with the last sampling being negative

*Neutralizing Positive*: At least one ADA-positive sample with neutralizing antibodies detected

- ADA-Negative Subject: A subject with no ADA-positive sample after the initiation of treatment

### **4.3.4 Outcomes Research**

#### **4.3.4.1 EuroQoL EQ-5D-3L**

Subjects' overall health status will be assessed using the EuroQoL Group's self-reported health status measure (EQ-5D-3L). EQ-5D-3L essentially has 2 components: the EQ-5D-3L descriptive system and the EQ visual analogue scale (EQ-VAS).

The EQ-5D-3L descriptive system comprises the following 5 dimensions: mobility, self-care, usual activities, pain/discomfort and anxiety/depression. Each dimension has 3 levels: no problems, some problems, and severe problems. Once the data have been collected and a database created, a scoring function can be used to assign a value (i.e., EQ-5D-3L utility index score) to self-reported health states from a set of population-based preference weights. For this study, EQ-5D-3L utility index values will be computed using a scoring algorithm based on the UK MVH-A1 TTO value set.

The EQ-VAS records the subject's self-rated health state on a 101-point visual analogue scale (0= worst imaginable health state; 100 = best imaginable health state).

A change from baseline of 0.08 for the EQ-5D-3L utility index score and of 7 for the EQ-5D-3L VAS are considered minimally important differences for the EQ-5D-3L.

#### **4.3.4.2 FACT-M**

The FACT-M questionnaire will be used to assess the effects of disease symptoms on functioning and well-being. The FACT-M includes the 27-items from the FACT General (FACT-G) to assess physical well-being (PWB; seven items), social/family well-being (SWB; seven items), emotional well-being (EWB; six items), and functional well-being (FWB; seven items). In addition, the FACT-M includes a 16-item disease-specific melanoma subscale (MS) and an 8-item melanoma surgery scale (MSS). The GP5 item, which will also be analyzed on its own is: "I am bothered by side effects of treatment".

Each FACT-M item is rated on a 5-point scale ranging from 0 (not at all) to 4 (very much). Scores for the PWB, FWB, SWB, and EWB subscales can be combined to produce a FACT-G total score, which provides an overall indicant of generic quality of life, while the FACT-G and MS scores can be combined to produce a total score for the FACT-M, which provides a composite measure of general and targeted quality of life.

A variant of the total score that is often more sensitive to physical and functional outcomes, the Trial Outcome Index, can be derived by summing the PWB, FWB, and MS scores. All scores are scaled so that higher values indicate better functioning as well as lower symptom burden.

For any given scale, the minimally important difference represents the smallest difference in score that informed patients might perceive as important and that would warrant consideration of a change in management. With regard to the MS, the minimally important difference has been estimated as a change of 2-4 points. For this trial, we will use the midpoint of the range (i.e., a change  $\geq 3$  points) to define a minimally important change in MS score. This interpretation has been applied in previous investigations.

Data will be scored according to the algorithm described in the FACT-M scoring manual.

If there are missing items, subscale scores can be prorated. This can be done using the following formula:

$$\text{Prorated subscale score} = [\text{Sum of item scores}] \times [\text{N of items in subscale}] \div [\text{N of items answered}]$$

When there are missing data, prorating by subscale in this way is acceptable as long as more than 50% of the items were answered. The total score is then calculated as the sum of the un-weighted subscale scores. The FACT scale is considered to be an acceptable indicator of patient quality of life as long as overall item response rate is greater than 80% (e.g., at least 22 of 27 FACT-G items completed). This is not to be confused with individual subscale item response rate, which allows a subscale score to be prorated for missing items if greater than 50% of items are answered. In addition, a total score should only be calculated if ALL of the component subscales have valid scores.

#### **4.3.4.3 WPAI:GH**

The WPAI:GH is a 6-item measure of impairment in work productivity and usual activities. Responses to the questionnaire's items are used to derive a score measuring the amount of absenteeism (work time missed), presentism (impairment at work/reduced on-the-job effectiveness), work productivity loss (overall work impairment/absenteeism plus presentism), and daily activity impairment attributable to general health. Outcomes are expressed as impairment percentages with higher numbers indicating greater impairment or less productivity.

Data will be scored according to the algorithm as described in the WPAI:GH scoring manual. Questions:

- 1 = currently employed
- 2 = hours missed due to health problems
- 3 = hours missed other reasons
- 4 = hours actually worked
- 5 = degree health affected productivity while working
- 6 = degree health affected regular activities

Multiply scores by 100 to express in percentages.

- Percent work time missed due to health:  $Q2/(Q2+Q4)$
- Percent impairment while working due to health:  $Q5/10$
- Percent overall work impairment due to health:  $Q2/(Q2+Q4)+[(1-Q2/(Q2+Q4)) \times (Q5/10)]$
- Percent activity impairment due to health:  $Q6/10$

## 5 SAMPLE SIZE AND POWER

The sample size for the study is based on a primary endpoint of PFS using BICR for either a Phase 2 or a Phase 3 study. The sample size for the Phase 2 study as justified below is approximately 400 randomized participants. The sample size for the Phase 3 study as justified below is 700 randomized participants, comprised of the Phase 2 population and an additional 300 participants.

The Phase 2 portion of the study serves multiple purposes. First, it enables the decision whether there is sufficient signal of efficacy in an all-comers population to proceed seamlessly to Phase 3. This PFS IA will be performed on the Phase 2 population when at least 150 events have been observed or all Phase 2 participants have been followed for at least 12 weeks. Second, if the PFS IA does not indicate moving to Phase 3 in an all-comers population, the final Phase 2 analyses will include the analyses of biomarker subgroups. Third, if the PFS IA indicates enrollment should be re-opened, the Phase 2 population will be part of the subsequent Phase 3 analyses.

The overall alpha for the Phase 3 study is 0.05 (two-sided). An administrative alpha penalty of 0.001 will be used for the PFS IA, although there is no plan to stop for efficacy at that analysis. If PFS IA meets the pre-specified threshold ( $HR \leq 0.8$ ) and the study proceeds to Phase 3, the final PFS analysis (PFS FA) will be performed when at least 365 PFS events have occurred per BICR and will use all remaining unspent alpha (0.049).

Note: on 26AUG2019 the study proceeded to phase 3 following the interim PFS analysis. This indicated that the HR was  $\leq 0.8$ .

### 5.1 Sample Size Justification for Phase 2 PFS Estimation

The primary objective of the Phase 2 portion of the study is to demonstrate preliminary clinical evidence of the treatment effect, measured by PFS, as determined by BICR using RECIST v1.1 in randomized participants with unresectable or metastatic melanoma treated with BMS-986213 compared to those treated with nivolumab monotherapy. The number of events is based on results from study CA209067 with a median PFS of 6.9 months for nivolumab monotherapy and 11.8 months for nivolumab with relatlimab. With 183 events, there will be approximately 80% power to detect a hazard ratio ( $HR$ ) = .73 with a type 1 error of 0.1 (1-sided). The cure rates were assumed to be 30% in the nivolumab arm and 40% in the nivolumab with relatlimab arm. The power is also affected by non-proportional hazards, since it is driven by the number of events, not the number of study participants, and some fraction of the participants in each arm are assumed will remain event-free for the duration of the study. Approximately 400 participants will be randomized to the Phase 2 study to ensure enough power to analyze the biomarker subgroups (see section below on the secondary endpoint of ORR in subgroup).

An interim analysis of PFS (PFS IA) will be performed when a minimum follow-up of 12 weeks is achieved for approximately 400 randomized participants or at least 150 PFS events have been observed using BICR. This analysis will include all available data at the time and will be performed by the DMC to maintain blinding of the sponsor. If the recommendation of the DMC is to proceed to the Phase 3 portion of the study then the study will start to re-enroll and the final PFS analysis for Phase 2 will not be performed.

Based on an anticipated screen failure rate of 30%, approximately 575 participants will need to be screened in order to randomize approximately 400 participants who fit the eligibility criteria.

### 5.1.1 Phase 2 Testing Strategy

If the interim PFS indicates the study will stop at Phase 2 (PFS HR > 0.8), the study will not enroll any additional participants, but members of the immediate study team (site-facing BMS team members) will remain blinded until the data are sufficiently mature (183 PFS events per BICR and a minimum 6 months of follow-up). The final Phase 2 analysis includes multiple subgroups of interest. The Benjamini-Hochberg method will be used to account for multiplicity by controlling the False Discovery Rate (FDR) when making comparisons in multiple subgroups.

### 5.1.2 Sample Size Justification for Secondary Objective of Subgroup Comparison in Phase 2 Trial

If the PFS IA does not support continuing to a Phase 3 study, the study will complete as a Phase 2 trial. The primary objective of the Phase 2 study using patients with previously untreated, unresectable or metastatic melanoma is to assess preliminary clinical evidence of the treatment effect measured by PFS as determined by BICR that may represent substantial improvement over available therapies. As a secondary objective, the Phase 2 will examine ORR information in biomarker subgroups based on LAG-3 expression ( $\geq 1\%$  expression versus  $< 1\%$  expression) and PDL-1 status ( $\geq 1\%$  tumor cell surface expression versus  $< 1\%$  tumor cell surface expression/non-quantifiable). ORR information and biomarker prevalence rates (for LAG-3 positive and negative expression, and for PDL-1 positive and negative status) used in the sample size calculations were based on information from study CA209067 and interim information from study CA224020. Table 5.1.2-1 shows the power for varying ORRs and varying prevalence rates for subgroups, assuming a Type 1 error rate of 0.1 (one-sided) and an overall N of 400 subjects. The Benjamini-Hochberg procedure will be used to control the False Discovery Rate (FDR) when testing multiple subgroups.

**Table 5.1.2-1: Power for Subgroups with Different N and Prevalence**

Overall N for Phase 2 Study	Subgroup N	Subgroup ORR	Subgroup Prevalence	Power (one-sided alpha .1 and 20% delta)
400	200	0.7	0.5	0.991
	140	0.7	0.35	0.962
	50	0.5	0.125	0.576
	80	0.5	0.2	0.72
	50	0.33	0.125	0.57
	80	0.33	0.2	0.713
	100	0.23	0.25	0.815
	120	.23	0.3	0.865

## 5.2 Sample Size Justification for Phase 3 PFS Comparison

The sample size is calculated in order to compare PFS among participants randomized to receive BMS-986213 versus nivolumab. The number of events required is simulated based on results from study CA209067 with a median PFS of 6.9 months for nivolumab monotherapy and 11.8 months for nivolumab with relatlimab, incorporating 35% of subjects with durable response in the combined groups, and a piecewise hazard ratio resulting in an effective hazard ratio of approximately 0.73.

Based on these assumptions, the study requires at least 365 PFS events to ensure approximately 85% power to detect a hazard ratio of 0.73 with an overall type I error of 0.05. Approximately 700 participants will be randomized to the two treatment arms in a 1:1 ratio. The final PFS analysis is planned to occur when 365 participants have had a PFS event. Total enrollment will take approximately 27 months (including a potential 6-month pause due to the PFS IA).

[figure not shown]
Based on an anticipated screen failure rate of 30%, approximately 1000 participants will need to be screened in order to randomize 700 participants who meet the eligibility criteria.

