The sample size is calculated in order to compare PFS among participants randomized to receive BMS-986213 versus nivolumab. The number of events required is simulated based on results from study CA209067, with a median PFS of 6.9 months for nivolumab monotherapy and 11.8 months for nivolumab with relatlimab, incorporating 35% of subjects with durable response in the combined groups, and a piecewise hazard ratio resulting in an effective hazard ratio of approximately 0.73.

Based on these assumptions, the study requires 365 PFS events to ensure approximately 85% power to detect a hazard ratio of 0.73 with an overall type I error of 0.05. Approximately 700 participants will be randomized to the two treatment arms in a 1:1 ratio. The final PFS analysis is planned to occur when 365 participants have had a PFS event per BICR. Total enrollment will take approximately 27 months (including a potential 6-month pause due to the interim PFS analysis).

Based on an anticipated screen failure rate of 30%, approximately 1000 participants will need to be screened in order to randomize 700 participants who meet the eligibility criteria.

Sample Size Justification for Secondary Objective of Overall Survival Comparison in Phase 3 Trial

The sample size is calculated in order to compare OS among participants randomized to receive BMS-986213 versus nivolumab. The number of OS events (deaths) required is based on results from study CA209067, with a median PFS of 36.9 months for nivolumab monotherapy and 49.2 months for nivolumab with relatlimab, resulting in an effective hazard ratio of approximately 0.75. With 300 deaths the power will be approximately 69% with a type I error rate of 0.05.

Sample Size Justification for Secondary Objective of Subgroup Comparison in Phase 2 Trial

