DOR is defined as the time between the date of first response to the date of first documented tumor progression (per RECIST v1.1) or death due to any cause. TTR is defined as the time from randomization to the date of the first documented CR or PR.	Summary of DOR with median (95% CI) and range (min, max) by K-M method. Summary of median Time to Response (mTTR) (95% CI)
PFS time and PFS rate as assessed by BICR, using RECIST v1.1 for subgroups	Summary of PFS with median (95% CI) by Kaplan-Meier method and PFS rate
OS is defined as the time between the date of randomization and the date of death due to any cause.	OS with median (95% CI) and range (min, max) by Kaplan-Meier method
Phase 2 Exploratory	Will be described in the SAP finalized before database lock

PFS is defined as the time between the date of randomization and the first date of documented progression, or death due to any cause, whichever occurs first. Participants who die without a reported progression will be considered to have progressed on the date of their death. Participants who did not progress or die will be censored on the date of their last evaluable tumor assessment. Participants who did not have any on study tumor assessments and did not die will be censored on their date of randomization. Participants who started anti-cancer therapy without a prior reported

progression will be censored on the date of their last evaluable tumor assessment prior to the initiation of subsequent anti-cancer therapy.

Phase 3 Testing Strategy

The Phase 2 part of the study will enroll approximately 400 participants. An interim analysis of PFS will be performed when a minimum follow-up of 12 weeks is achieved for approximately 400 randomized subjects or at least 150 PFS events have been observed using BICR.

- If the interim PFS analysis achieves the pre-specified threshold (as defined in the SAP and the DMC Charter), then the study will continue to Phase 3 and remain blinded.
- If interim PFS analysis does not achieve the pre-specified threshold (as defined in the SAP and DMC Charter) the study will not open enrollment to Phase 3. The Phase 2 data will be allowed to mature and then the sponsor will unblind for analysis. If that scenario takes place, approximately 575 participants will need to be enrolled in order to randomize 400 participants assuming a screen failure rate of 30%.

The overall alpha for the Phase 3 study is 0.05 (two-sided).

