**Figure 5.2.1-1: Phase 3 Hierarchical Procedure with Group Sequential Testing in All Randomized Subjects**

Approximately 700 subjects will be randomized in 1:1 ratio to BMS-986213 or nivolumab monotherapy arm respectively.

- Approximately 365 PFS events in all randomized subjects will provide around 85% power to detect an average HR of 0.73 with an overall type I error of 5.0% (two-sided). The target hazard ratio was obtained via simulation using above modeling.

Table 5.2.1-1 summarizes the analysis of PFS in Phase 3. The interim PFS analysis (PFS IA) will be performed when a minimum follow-up of 12 weeks is achieved for approximately 400 randomized subjects or at least 150 PFS events have been observed per BICR. PFS IA will determine whether the study stops at Phase 2 (PFS HR > 0.8) or continues as Phase 3 (PFS HR ≤ 0.8). An administrative alpha penalty of 0.001 will be used for the PFS IA, although there is no plan to stop for efficacy at that analysis.

If PFS IA meets the pre-specified threshold and the study proceeds to Phase 3, the final PFS analysis will be performed when at least 365 PFS events have occurred per BICR and will use all remaining unspent alpha.

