**Table 5.2.1-1: Schedule of Analyses of Primary Endpoint**

	Interim PFS Analysis (PFS IA)	Final PFS Analysis (PFS FA)
Population	All randomized subjects	
Conditions	When 150 events of PFS are observed or all Phase 2 randomized subjects have been followed for at least 12 weeks (time of 1st scan)	When 365 events of PFS are observed
Expected timing	~15 months	~34 months
Nominal significance level	.001	0.049
Critical Hazard Ratio	HR ≤ 0.8*	HR ≤ 0.81

\*Not formally tested (administrative alpha); had to pass this boundary for the study to continue to Phase 3.

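### The stated 85% Phase 3 PFS power matches the 365-event test taken alone and appears to leave out the required interim HR ≤ 0.8 rule; design-stage power with the rule is lower

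*SAP*

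**What the plan says.** Three places give the same power. SAP 5.2: "the study requires at least 365 PFS events to ensure approximately 85% power to detect a hazard ratio of 0.73". SAP 5.2.1: "Approximately 365 PFS events in all randomized subjects will provide around 85% power to detect an average HR of 0.73". Protocol 10.1: "the study requires 365 PFS events to ensure approximately 85% power to detect a hazard ratio of 0.73". SAP 5 sets the final PFS alpha at 0.049 two-sided, after an administrative 0.001 for the interim.

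The same documents make the final test conditional. SAP 5.2.1: "PFS IA will determine whether the study stops at Phase 2 (PFS HR > 0.8) or continues as Phase 3" (HR ≤ 0.8). The footnote to Table 5.2.1-1 says the study "had to pass this boundary for the study to continue to Phase 3". Protocol 10.2.2 says that if the threshold is missed ("as defined in the SAP and DMC Charter) the study will not open enrollment to Phase 3"). The interim trigger in Table 5.2.1-1 is "When 150 events of PFS are observed or all Phase 2 randomized subjects have been followed for at least 12 weeks", expected at about 15 months.

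None of the three power statements mentions the interim rule. The documents give neither the chance of passing it nor any power that includes it.

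**The concern.** The target HR of 0.73 is close to the cut-off of 0.8. With 150 to 200 interim events, an observed HR above 0.8 is quite likely even when the target effect is true. If it occurs, Phase 3 enrolment does not open and the 365-event test is never done. The chance, seen from the start, of a positive Phase 3 PFS result is therefore the chance of passing the interim and also being significant at 365 events. If 85% describes only the second step, a reader who takes it as the power of the Phase 3 design is given too favourable a figure.

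**Working it through.** **Inputs from the documents.** Final events 365, HR 0.73, 1:1 allocation (SAP 5.2). Final alpha 0.049 two-sided (SAP 5). Interim rule: observed HR ≤ 0.8 (SAP 5.2.1). Interim at 150 events or 12 weeks' follow-up of about 400 patients. Medians 6.9 and 11.8 months (SAP 5.2). Cure rates 30% and 40% (SAP 5.1, stated for Phase 2).

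**Step 1: reproduce the stated figure.** Power = Φ(√(D/4) × |ln HR| − z), with D = 365, |ln 0.73| = 0.3147 and z = 1.969:

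√(365/4) × 0.3147 − 1.969 = 9.552 × 0.3147 − 1.969 = 1.038, and Φ(1.038) = 0.850.

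The critical HR is exp(−1.969 × 2/√365) = 0.814, which agrees with the 0.81 in Table 5.2.1-1. The stated 85% is therefore matched with no interim rule in the calculation.

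**Step 2: add the rule under proportional hazards.** With d interim events, P(pass) = Φ((ln 0.8 − ln 0.73) × √d/2), where ln(0.8/0.73) = 0.0916. Joint power comes from the bivariate normal distribution of the interim and final statistics with correlation √(d/365). For d = 150: 0.0916 × √150/2 = 0.561, Φ(0.561) = 0.713, correlation 0.641, joint power 0.668.

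| Interim events | P(pass) | Joint power | Power given a pass | Loss against 85.0% |
|---|---|---|---|---|
| 150 | 71.3% | 66.8% | 93.7% | 18.2 points |
| 190 | 73.6% | 69.7% | 94.7% | 15.3 points |
| 200 | 74.1% | 70.4% | 94.9% | 14.6 points |

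Joint power cannot exceed P(pass), so more final events cannot restore 85%.

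**Step 3: cure model.** I assumed that the Phase 2 cure rates also hold in Phase 3: S(t) = c + (1 − c)exp(−λt), with λ = 0.1816 and 0.1518 per month, which gives the stated medians. Accrual was also assumed: the first 400 patients over 9, 12 or 15 months, a 6-month pause, and the last 300 over 12, 9 or 6 months. Each sums to the SAP's total: "Total enrollment will take approximately 27 months (including a potential 6-month pause due to the PFS IA"). There were 8000 simulated trials per case, with the interim at the 12-week trigger.

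| First 400 over | Interim month, events | P(pass) | Joint power | Final test alone | Like-for-like loss |
|---|---|---|---|---|---|
| 9 months | 11.7, 175 | 78.0% | 73.1% | 85.7% | 12.6 points |
| 12 months | 14.7, 189 | 78.1% | 74.0% | 86.4% | 12.4 points |
| 15 months | 17.7, 199 | 77.9% | 73.8% | 86.1% | 12.3 points |

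The 12-month case agrees with the expected 15 months in Table 5.2.1-1. A separate run of that case (3000 trials) gave joint power of 73.6% (loss 12.9 points) at the 12-week trigger and 70.1% (loss 15.0 points) at 150 events.

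**Step 4: delayed effect.** SAP 7.5.2 anticipates late separation of the curves. I assumed HR 1 for the first 1, 2 or 3 months and then 0.667, 0.583 or 0.484, so that the final HR stays near 0.73 and the final test alone keeps 84-86% power (accrual 12 + 6 + 9 months, 8000 trials).

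| Delay | Final test alone | Joint, 12-week trigger (loss) | Joint, 150 events (loss) |
|---|---|---|---|
| 1 month | 84.4% | 66.9% (17.5) | 60.6% (23.8) |
| 2 months | 85.8% | 65.7% (20.1) | 56.0% (29.8) |
| 3 months | 85.0% | 60.4% (24.6) | 47.2% (37.8) |

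The implied experimental medians are 12.2, 13.4 and 15.0 months. Among these delayed cases the 1-month delay is nearest the stated 11.8 months.

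**Step 5: type I error.** With HR 1, the chance of passing the interim and then winning is 1.39% at 150 interim events and 1.43% at 200, against 2.45% one-sided without the rule.

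**The case against.** The best reply is that 85% is attached to 365 events, is correct for 365 events, and is nowhere called the chance of success from the start of the trial. The Phase 2 outcome has its own power statement (183 events, about 80%), and the HR rule is stated openly. This stands to the extent that there is no arithmetic error: what is missing is an operating characteristic. It does not make 85% a conditional figure, because power given a pass is about 94-95%.

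The omission is also inferred. SAP 5.2 says the event number was simulated with piecewise hazards, and the simulation is not shown. The DMC Charter and DMC analysis plan are not available here, and the DMC is advisory in form. These are real limits. Still, the exact match in Step 1 leaves no room for the rule, and the footnote to Table 5.2.1-1 reads as binding.

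The interim timing is unsettled too. Under the cure model and accrual above, 150 events arrive at about 10.2, 12.1 or 14.1 months, before the 12-week trigger. If the earlier trigger applies, the 73-74% cases do not arise; the expected 15 months points to the later one. Recording progression only at scheduled scans would cut the events at the 12-week trigger to about 161, 177 and 189.

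Finally, both decisions are already made (SAP 5 and 5.2.1). That limits the severity, not the correctness.

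**Conclusion.** The point holds as a minor correction to a design-stage figure. The 85% is the power of the final 365-event test taken alone. It is neither the joint power of the design as written nor the power given a pass.

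The loss is about 15-18 points under proportional hazards with 150 to 200 interim events, about 12-13 points under the assumed cure model at the 12-week trigger, and about 18-38 points under the assumed 1 to 3 month delays. These are cases, not bounds. The size depends on the undisclosed piecewise hazards, the accrual and which interim trigger applies. The direction follows if the 85% does omit the rule, because an extra required condition cannot raise the chance of success.

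A reader might infer that the PFS result is weakened or its false-positive risk raised. The documents do not support that: the interim rule was passed on 26AUG2019, the final PFS test was significant on 09MAR2021, and the rule lowers the false-positive rate. A reader might also infer one fixed loss; the range of cases above rules that out.

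**What to change.** In Protocol 10.1 and SAP 5.2 and 5.2.1, label the 85% as *power of the final 365-event test taken alone*. Add three rows to SAP Table 5.2.1-1, marked as design-stage figures: probability of passing the HR ≤ 0.8 rule, joint power (pass and significant at 365 events), and power given a pass. Compute them with the sponsor's own piecewise simulation model at the planned interim timing, and state which trigger that timing assumes.

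The cost is a rerun of the simulation with the rule added, a document update, and a less favourable stated power. The Protocol change history shows that the sponsor has already simulated interim endpoints against the final PFS test, though not that the event simulation can be reused unchanged. Under Protocol Appendix 2, a protocol edit needs IRB/IEC approval as an amendment, or IRB/IEC notice if made by administrative letter. No patients are added, and no test, alpha, boundary or decision changes.
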